### 2.9.1 Eligibility assessment

Patients are considered eligible for this study if they meet **all** the inclusion criteria and **none** of the exclusion criteria as defined in **Section 2.8**. The principal investigator or subinvestigator at each investigational center will determine patient eligibility based on the inclusion/exclusion criteria.

All potential subjects must have a CT scan (without contrast) of the temporal bone done within 6 months before study enrollment. The CT scan must include coronal and axial images of the temporal bone including the Eustachian tube. Two electronic copies in DICOM format of the CT scan must be available; 1 copy to be retained by the investigational center and 1 copy to be retrieved by the sponsor.

### 2.9.2 Baseline visit

All candidates for the study will have the following baseline clinical evaluations done **before enrollment and randomization**:

- Informed consent signed
- Baseline medical history, demographics, symptoms, and medication history in the 12-month period before enrollment
- Eligibility assessment: subjects meet all inclusion and no exclusion criteria.
- Nasal endoscopy
- Otoscopy examination
- Tympanometry
- Valsalva evaluation

- Assessment of ear infections over the 12-month period before enrollment
- Audiologic examination including a pure tone auditory (PTA) test
- EQ-5D and ETDQ-7 QOL questionnaires (completed by the study subject)
- Pregnancy test for female subjects of childbearing potential

The results of all baseline evaluations will be documented on the appropriate Case Report Forms (CRFs).

For subjects undergoing balloon dilation, preprocedure antibiotics and steroids may be prescribed at the discretion of the study physician. Medications may be prescribed to treat active infections and procedures may be rescheduled until active infections resolve.

### 2.9.3 Enrollment

A patient will be considered enrolled in the study after the baseline assessment once all the inclusion/exclusion criteria have been met and at the time of randomization.

### 2.9.4 Randomization

Randomization assignments will be generated by an independent statistician using a distribution in variable blocks sizes for each center with a 1:1 allocation to control or balloon dilation. The master randomization list will be stored by the Sponsor. Randomization assignments will be placed into sequentially numbered and sealed envelopes. The trained study center personnel will contact Sponsor to receive the randomization assignment after the following steps have been completed:

1. All baseline evaluations have been performed
2. Subject has been determined eligible for the study (ie, inclusion/exclusion criteria reviewed)
3. Subject has signed an Informed Consent

The Sponsor will retrieve the first (or next) sequentially numbered envelope for that center and open it. The randomization assignment, including the randomization ID number and treatment assignment, will be recorded on the Randomization Enrollment Case Report Form. The Sponsor personnel will record the subject ID in the randomization log.

### 2.9.5 Control arm assignment

Subjects randomized to the control arm will continue their current ETD medical treatment regimen for 6 weeks after randomization. A treatment regimen consisting of no medication is permitted if consistent with the subject's current treatment plan. Medications will be documented on the Medications CRF. Control subjects are not allowed to undergo any surgical treatments during this study period.

After the 6-week period of continued medical therapy, control subjects who continue to have ETD symptoms (defined as an overall ETDQ-7 score  $\geq 3.0$  or a change of  $< 0.4$ ) will be allowed to crossover to balloon dilation treatment and will undergo the dilation procedure and postprocedure follow-up visit schedule for the balloon dilation arm. Control subjects who do not

crossover will be exited from the study at this time. The 6-week crossover evaluation will serve as the preprocedure assessment for crossover subjects.

#### 2.9.6 Balloon dilation arm assignment and procedure

Subjects should undergo the balloon dilation procedure within 60 days of the baseline assessment (randomized to balloon dilation) or the 6-week crossover evaluation (crossover subjects). All female subjects of childbearing potential are required to have a negative blood or urine pregnancy test **within 10 days before a balloon dilation procedure**.

Refer to the XprESS Instructions for Use (IFU) for specific instructions on system preparation, subject preparation, device set-up, shaping the device, and detailed treatment procedure for using XprESS to perform Eustachian tube dilation.

#### *Procedure site of service*

Investigators may choose to complete study procedures under general plus local anesthesia in a surgical setting or under local anesthesia alone in the office setting based on their medical discretion and subject tolerance. If the study procedure is first attempted in the office setting but cannot be completed under local anesthesia alone due to subject tolerance, the subject may be treated under general anesthesia in a surgical setting without being withdrawn from the study. Such cases will not be considered treatment failures. Procedures converted from local anesthesia alone to general anesthesia will be documented on the Procedure CRF.

#### *Procedure anesthesia*

Anesthesia should be administered appropriately to allow subject tolerance and based on the treating physician's medical training. Physicians may choose to use general and/or local anesthesia regimens that will allow safe and tolerable use of the device in the subject. Type of anesthesia and location of local injections will be documented.

#### *Eustachian tube assessment*

A temporal CT scan with axial and coronal views performed within the last 6 months before study enrollment will be reviewed to ensure there are no anatomic anomalies that would prevent transnasal access to the Eustachian tube or put the subject at increased risk (eg, dehiscence of the carotid artery). If such conditions exist, the subject is not eligible for the study.

#### *Device size selection*

Investigators may choose the XprESS device size based on their medical knowledge and the subject's Eustachian tube anatomy. All balloon sizes are appropriate for treating Eustachian tubes; selection is based on physician preference. The XprESS device sizes are listed in **Section 4.1**.

#### *Eustachian tube balloon dilation*

The XprESS balloon is designed for a transnasal approach only. Procedural information on device use is provided in the XprESS IFU.

The following data will be collected during the study procedure and documented on the appropriate CRFs:

- Site of service
- Admission and discharge date/times
- Procedure start/stop times
- Type of anesthesia and location and dosage of any local injections
- Identification of all XprESS devices used
- Technical success for XprESS device
- Total number of balloon inflations for each treatment side
- Total duration of balloon inflations (in seconds) for each treatment site
- Procedures that convert from local anesthesia alone to general anesthesia
- Procedure pain score (for subjects treated under local anesthesia alone; not required for subjects who are treated under general anesthesia)
- Adverse events
- Device malfunctions

#### *Postprocedure care*

Postprocedure care, including medical management, is at the discretion of the physician. Postprocedure medical and clinical management will be collected on the Medication CRF at the 6-week postprocedure visit.

#### *Concomitant procedures*

Concomitant procedures are not allowed in this study. Specifically, subjects randomized to the control arm are not allowed to undergo any surgical procedures of the ears or sinuses during the 6-week period of continued medical therapy.

#### 2.9.7 Follow-up visits

Subjects randomized to the control arm are scheduled for a follow-up visit at 6 weeks ( $\pm 7$  days) after their randomization. At this visit, control subjects will be evaluated and if their ETD symptoms persist (defined as overall ETDQ-7 score  $\geq 3$  or change  $< 0.4$ ), the subjects are eligible for crossover to balloon dilation treatment. Subjects who do not have persistent ETD symptoms are exited from the study after completion of this visit.

Subjects randomized to balloon dilation and crossover subjects are scheduled for the following postprocedure follow-up visits (window):

- 6-Week ( $\pm 7$  days)
- 3-Month ( $\pm 15$  days)
- 6-Month ( $\pm 30$  days)
- 12-Month ( $\pm 45$  days)

The following assessments are required at all follow-up visits:

- Symptom assessment
- Nasal endoscopy examination
- Otoscopy examination

- Tympanogram
- Valsalva evaluation
- Medication use since last study visit
- Ear infections since last study visit
- Revision dilation or additional surgery
- Subject satisfaction
- EQ-5D
- ETDQ-7
- Adverse events

In addition to the assessments noted above, an **audiologic examination is required at the 6-month visit.**

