## Investigational Plan Summary

Title:	XprESS Eustachian Tube Dilation Study
Study device:	XprESS™ Multi-Sinus Dilation System (XprESS device)
Study design:	A prospective, multicenter, 2-phase, controlled study. Phase 1 consists of a nonrandomized design. Phase 2 consists of a randomized design.
Enrollment:	A total of 50 subjects: Phase 1 – 10 nonrandomized balloon dilation subjects Phase 2 – 40 subjects randomized 1:1 to balloon dilation (treatment) or continued current medical therapy (control)
Treatment:	Phase 1: All subjects will receive balloon dilation Phase 2: Subjects will be randomized 1:1 to the following study arms: 

1. Control arm: Continued current medical management with ability to crossover to dilation after 6 weeks, if not improved

2. Treatment arm: Eustachian tube dilation – bilateral or unilateral, as indicated

Clinical centers:	Up to 7 US investigational centers
Inclusion criteria:	Subjects MUST : 

1. Be <math>\geq 18</math> years old

2. Have been diagnosed with Eustachian tube dysfunction (ETD) for no less than 12 months before enrollment with 3 or more of the following symptoms: ear pain, ear pressure, ringing in the ears, cracking or popping sounds in the ears, muffled hearing, or feeling that ears are clogged or “under water”

3. Have an overall ETDQ-7 score <math>\geq 3.0</math>

4. Have a record of failed medical management for ETD consisting of a minimum of either 4 weeks of daily intranasal steroid spray or 1 completed course of an oral steroid within the 12-month period before enrollment

5. Be a candidate for unilateral or bilateral transnasal balloon Eustachian tube dilation using the XprESS device

6. Have a temporal bone CT scan (showing the Eustachian tube) without contrast within 6 months of the enrollment date

7. Be able to read and understand English

8. Be able and willing to provide consent

9. Be willing to comply with the protocol requirements

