## 2 Protocol

### 2.1 Study design

The study is a prospective, multicenter, 2-phase, controlled study. Phase 1 will include 10 subjects treated with balloon dilation.

Phase 2 will include 40 subjects randomized 1:1 to balloon dilation or control (6 weeks of continued current medical therapy). Phase 2 is designed to test the primary efficacy endpoint hypothesis that ETD symptom improvement (overall ETDQ-7 score) after balloon dilation is superior to the control group. For subjects randomized to the control arm, if ETD symptoms persist at 6 weeks after randomization (overall ETDQ-7 score  $\geq 3.0$  or change  $< 0.4$ ), the subjects will be allowed to crossover to the balloon dilation arm. Control subjects who do not have persistent ETD symptoms at 6 weeks after randomization will be exited from the study. **Figure 1** presents the study design and subject flow for Phase 2.

[figure not shown]

Figure 1. Phase 2 Study Design and Subject Flow

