## 2.5 Study hypothesis

The study is designed to test the primary efficacy endpoint hypothesis that ETD symptom improvement after balloon dilation is superior to the control group.

The following hypothesis will be tested in the comparison of mean change from baseline in overall ETDQ-7 scores at 6 weeks using a 1-sided Student's t-test where a p value less than 0.025 will be considered statistically significant:

Ho:  $d \geq 0$

Ha:  $d < 0$

Where  $d$  is the difference between balloon dilation and control group (balloon dilation – control) for the mean change from baseline to 6 weeks in the overall ETDQ-7 score.

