## 2.6 Sample size estimation

The sample size was calculated using PASS, Inequality Tests for Two Means (2-sample t-test) to test for superiority of improvement of ETDQ-7 scores at 6 weeks and was based on the following assumptions:

- Significance level (1-sided alpha) = 0.025
- Power = 80%
- Mean change in overall ETDQ-7 score in the balloon dilation group = -2.15
- Mean change in overall ETDQ-7 score in control group = -0.85
- Common standard deviation for both groups = 1.3

Under the assumptions outlined above, a total sample size of 34 randomized subjects (17 per arm) is adequate to test this hypothesis. To account for up to 10% attrition, a minimum of 40 subjects will be enrolled in Phase 2 of the study.

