### 2.8.1 Inclusion criteria

Subjects MUST:

1. Be  $\geq 18$  years old
2. Have been diagnosed with ETD for no less than 12 months before enrollment with 3 or more of the following symptoms: ear pain, ear pressure, ringing in the ears, cracking or popping sounds in the ears, muffled hearing, or feeling that ears are clogged or “under water”
3. Have an overall ETDQ-7 score  $\geq 3.0$
4. Have a record of failed medical management for ETD consisting of a minimum of either 4 weeks of daily intranasal steroid spray or 1 completed course of an oral steroid within the 12-month period before enrollment
5. Be a candidate for unilateral or bilateral trans-nasal balloon Eustachian tube dilation using the XprESS device
6. Have a temporal bone CT scan (showing the Eustachian tube) without contrast within 6 months of the enrollment date
7. Be able to read and understand English
8. Be able and willing to provide consent
9. Be willing to comply with the protocol requirements

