#### 2.10.1 Primary and secondary endpoint assessments

##### *Mean change in overall ETDQ-7 score*

The Eustachian Tube Dysfunction Questionnaire (ETDQ-7) is a standardized, 7-item questionnaire designed to assess quality of life associated with Eustachian tube dysfunction. The 7 dimensions of the questionnaire are pressure, pain, feeling clogged, cold/sinusitis problems, crackling/popping, ringing, and feeling muffled. Each item is assessed on a 1 (no problem) to 7 (severe problem) scale and an overall score, which is the mean of the 7 dimension scores, is calculated. The questionnaire is designed to be self-completed by the subject. ETDQ-7 questionnaires will be completed at baseline and at all study visits. Changes in overall ETDQ-7 scores will be based on the mean change between the baseline assessment (or 6-week crossover

evaluation for crossover subjects) and each follow-up assessment. Standard treatment effect size may also be calculated for the mean overall ETDQ-7 score. The ETDQ-7 CRF may be considered a source document if completed directly by the subject on the CRF.

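### Does the 6-week crossover rule leave no control subject who can be exited as improved?

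*Combined protocol and SAP*

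**What the plan says.** The rule appears in Sections 2.1, 2.9.5 and 2.9.7. At 6 weeks after randomization a control has persistent symptoms if the overall ETDQ-7 score is at least 3.0 or the change is below 0.4. Those controls may cross over; in the words of Section 2.9.7, "the subjects are eligible for crossover to balloon dilation treatment. Subjects who do not have persistent ETD symptoms are exited from the study". For the rest, Section 2.1 states: "Control subjects who do not have persistent ETD symptoms at 6 weeks after randomization will be exited from the study". The Investigational Plan Summary puts the control arm more briefly: "Continued current medical management with ability to crossover to dilation after 6 weeks, if not improved". None of these places says whether change is signed, absolute, or an amount of improvement.

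Four other statements bear on the reading:

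- **Entry floor.** Section 2.8.1, criterion 3: "Have an overall ETDQ-7 score" of at least 3.0.
- **Scale.** Section 2.10.1: "Each item is assessed on a 1 (no problem) to 7 (severe problem) scale". The overall score is the mean of seven items, so higher is worse.
- **Planning means.** Section 2.6: "Mean change in overall ETDQ-7 score in the balloon dilation group = -2.15" and "Mean change in overall ETDQ-7 score in control group = -0.85". Improvement is negative here.
- **Hypothesis.** Section 2.5 defines d as dilation minus control "for the mean change from baseline to 6 weeks in the overall ETDQ-7 score", with d below zero favouring dilation.

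**The concern.** The only place where the plan attaches a sign to a change in ETDQ-7 is the hypothesis and sample-size text, where improvement is negative. If that sign is carried into the crossover rule, the rule fails. To be exited as improved, a control would need a score below 3.0 and a change of at least +0.4, that is, a worsening. A subject who entered at 3.0 or above cannot have both. Even a fall from 7.0 to 1.0, a change of -6.0, would count as persistent.

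The rule governs which of the 20 planned controls may receive an investigational procedure whose listed risks (Section 3.2) include permanent hearing loss and carotid artery damage. Section 2.10.1 also takes the 6-week crossover evaluation as the starting point for a crossover subject's later changes. A control crossed over with a low score would have little room to improve, which could dilute the secondary ETDQ-7 result if crossovers are counted among the dilation subjects. If centers read the rule differently, crossover groups would differ by center.

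**Working it through.** **1. The plan's own figure.** The crossover rule has no stated numerical result. The figure that carries the sign convention is the sample size in Section 2.6. The planned difference is d = -2.15 - (-0.85) = -1.30, and with SD 1.3 the standardized size is 1.30/1.3 = 1.0. For a t-test at one-sided 0.025, the noncentrality is 1.0 × √(n/2):

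- n = 16 per arm: √8 = 2.83, power 78.1%
- n = 17 per arm: √8.5 = 2.92, power 80.7%

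So 17 per arm, 34 in total, is reproduced. In that section improvement is clearly negative.

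**2. Possible scores.** Seven items scored 1 to 7 give a sum S from 7 to 49, and the overall score is S/7. The entry floor of 3.0 means a baseline sum S0 of 21 to 49 (29 values). The 6-week sum S6 can be 7 to 49 (43 values). Possible pairs: 29 × 43 = 1,247.

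**3. Change read as follow-up minus baseline.** Exit requires S6 ≤ 20 and (S6 - S0)/7 ≥ 0.4. With S0 ≥ 21 and S6 ≤ 20, the change is at most -1/7 = -0.14. No pair meets both conditions: 1,247 qualify and 0 exit.

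**4. Change read as amount of improvement (baseline minus follow-up).**

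- Qualify by score (S6 from 21 to 49): 29 × 29 = 841.
- Pairs with S6 ≤ 20: 29 × 14 = 406.
- Of these, the change limb keeps those with S0 - S6 < 0.4 × 7 = 2.8, so a drop of 1 or 2 points. There are three: 21 to 20, 21 to 19 and 22 to 20 (scores 3.00 to 2.86, 3.00 to 2.71, 3.14 to 2.86).
- Qualify in total: 841 + 3 = 844. Exit: 406 - 3 = 403.

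**5. Change read as absolute.** At 3.0 or above, the first limb already decides. Below 3.0 every change is a drop, so its absolute size equals the improvement. The result is identical to step 4 for all 1,247 pairs.

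**6. From pairs to patients.** Score pairs are not equally likely, so 403 of 1,247 is not a patient proportion. As an illustration, take the plan's control change (mean -0.85, SD 1.3) as normal and independent of baseline. The documents give no baseline distribution, so a normal baseline cut to the range 3 to 7 is assumed:

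| Assumed baseline mean, SD before truncation | Mean after truncation | Exit, improvement reading | Of 20 controls | Kept by the 0.4 limb alone |
|---|---|---|---|---|
| 4.0, 0.8 | 4.16 | 41.1% | 8.2 | 0.7% |
| 4.5, 1.0 | 4.62 | 31.0% | 6.2 | 0.4% |
| 5.0, 1.0 | 5.00 | 23.2% | 4.6 | 0.2% |

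The signed and improvement readings disagree only on the exit group, roughly 5 to 8 of 20 controls under these assumptions. At any score of 3.0 or above they agree.

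**The case for a change.** The best case for an amendment does not depend on anyone adopting the signed reading. Once change is taken as improvement, the 0.4 limb is almost idle, adding three pairs to 841. That suggests the rule was not written as intended. A control who falls from 6.0 to 3.0 still counts as persistent, which sits awkwardly with the summary's condition that the subject has not improved. Table 1 ticks an eligibility assessment at the crossover visit without saying whether the entry score is applied again. If it is, the change limb can admit nobody. Since the rule opens the way to an invasive procedure and the correction is only wording, why leave it to inference?

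Part of this stands. The direction of change is not written down, and the plan would be tidier if it were. The rest does not show a contradiction. A limb that adds little is redundant: it catches subjects who entered at 3.00 or 3.14 and dipped just under 3.0. A control at exactly 3.0 is still at the study's own entry threshold, so calling the symptoms persistent is coherent. The summary's phrase is shorthand for a rule given in full three times, and a wish for a different treatment of large improvers is a preference about the threshold. The tick in Table 1 may mean crossover eligibility only. If it carries its Section 2.9.1 meaning, it is a further barrier to crossing over a control whose symptoms resolved.

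**Conclusion.** The arithmetic behind the worry is right, but its premise is not secure. Section 2.5 defines a between-group difference of means and Section 2.6 lists two planning means. Neither defines an individual subject's change for crossover, and Section 2.10.1, which describes how ETDQ-7 changes are taken, gives no sign. In a sentence defining persistent symptoms, with a positive 0.4 and an express route out for controls without them, change is naturally an amount of improvement. The absolute reading gives the same classification for every possible score. Centers would diverge only if some adopted the one reading that makes the exit instruction impossible, and nothing in the text points them to it.

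The reach is also limited. The control arm's primary outcome is recorded at the 6-week evaluation, before any crossover procedure, so the sample size of 34, the power and the one-sided 0.025 level do not move. Crossover is permitted, not required, and controls who decline it still leave the study. Section 2.4 does not expressly place crossover subjects in the pooled dilation cohort, so any effect on the secondary results is inferred.

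This is a gap in detail that sites and analysts fill sensibly, and no change to the plan is called for. The conclusion assumes that controls met the entry floor of 3.0 and have a 6-week score. The illustration of 5 to 8 controls rests on assumed baselines. Which subjects the rule was meant to cover remains the sponsor's decision.

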#### 2.9.8 Revision dilations or additional surgery

Revision dilations or other surgical procedures are permitted for subjects who do not experience relief of ETD symptoms after balloon dilation treatment. However, it is recommended that revision procedures are not performed before the majority of tissue healing/remodeling has been allowed to occur. This process can take up to 3 months after the initial procedure. Standard of care medical treatment is permitted at any time during the study to address subject symptoms.

If a subject has a revision dilation or additional ENT surgery during the postprocedure follow-up period, the investigational center should make every effort to collect the procedure/operative notes for the procedure(s). The date and type of procedure performed will be documented on the Revision Dilation/Additional Surgery CRF. A copy of the deidentified revision procedure notes will be retrieved for the sponsor study files.

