### 2.3.2 Secondary endpoints

The following measures will be collected as secondary endpoints:

- Mean change in overall ETDQ-7 score from baseline to follow-up (balloon dilation subjects)
- Technical success rate
- Revision dilation rate

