## 2.7 Data analyses

Summary statistics will be calculated for all study endpoints. Categorical variables will be summarized using frequency distributions and continuous variables will be summarized with means, standard deviations, and ranges. Confidence intervals (95% CI) may be computed for select study endpoint measures. The primary efficacy endpoint will be tested at a 1-sided alpha level of 0.025. The secondary endpoint of the mean change in the overall ETDQ-7 score from baseline to follow-up in subjects treated with balloon dilation will be tested at a 2-sided alpha level of 0.05.

Subjects who are randomized but drop out before receiving their randomized treatment (balloon dilation or completion of the 6-week continued medical therapy) will not be included in the data analysis.

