#### *Revision dilation rate*

Revision dilation is defined as any repeat balloon dilation procedure performed on an ET that was initially treated with an XprESS device. The parameter of interest is the percent of subjects who experience 1 or more revision dilations during the study.

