### 3.3 Risk mitigation

The protocol has been developed to minimize the risks for the subject in a number of ways. Sample size was calculated to expose the smallest number of subjects while still being able to adequately test the study objectives. The subject selection criteria were designed to minimize risk by excluding patients who have comorbidities or conditions that may put the patient at higher risk for the balloon dilation procedure. Concomitant procedures that could increase risk and confound study results are not permitted during the study. The subjects are closely monitored by frequent follow-up visits during the study. Finally, the selected investigators are experienced in endoscopic surgery, specifically trained on use of the XprESS device, and expected to comply with the manufacturer's IFU for the XprESS device for Eustachian tube dilation.

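### The 3-, 6- and 12-month ETDQ-7 change includes scores taken after further surgery, and surgery other than repeat dilation enters no efficacy endpoint

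*Combined protocol and SAP*

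**What the plan says.** **Further surgery is allowed.** Section 2.9.8: "Revision dilations or other surgical procedures are permitted for subjects who do not experience relief of ETD symptoms after balloon dilation treatment". On timing, "it is recommended that revision procedures are not performed before the majority of tissue healing/remodeling has been allowed to occur"; the section adds that healing can take up to 3 months. This is advice, not a bar. On recording, "The date and type of procedure performed will be documented on the Revision Dilation/Additional Surgery CRF". Table 1 and Section 2.9.7 collect further surgery at every postprocedure visit.

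**ETDQ-7 change.** Section 2.7 names "The secondary endpoint of the mean change in the overall ETDQ-7 score from baseline to follow-up in subjects treated with balloon dilation" and tests it at 2-sided 0.05. Section 2.10.1 bases the change on the baseline score (the 6-week crossover evaluation for crossover subjects) and each follow-up score. Neither section says what happens to a score that follows further surgery. Section 2.7.2 promises missing-data analyses for the primary efficacy endpoint only. Section 2.9.10 keeps dilated subjects in the study to 12 months.

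**Retreatment.** Section 2.10.1: "Revision dilation is defined as any repeat balloon dilation procedure performed on an ET that was initially treated with an XprESS device". The rate is the percent of subjects with at least one such procedure during the study.

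**Related rules.** For the first 6 weeks in the control arm, Section 2.9.5 says: "Control subjects are not allowed to undergo any surgical treatments during this study period". Section 3.3 says: "Concomitant procedures that could increase risk and confound study results are not permitted during the study".

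**The concern.** Surgery is permitted specifically for subjects whose dilation did not give relief. Their later scores enter the mean by default, because the definition takes each follow-up score and nothing excludes those after surgery. If the surgery helps, the poorest results at later visits are the ones that improve, and the reported change after dilation improves with them.

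The endpoint that should reveal this is narrow. A subject who gets ear tubes, or who was treated on one side and later has a first dilation of the other ear, does not count as revised. Section 2.9.8 does not name ear tubes, but exclusion criterion 1 lists ear tube placement among prior surgeries, so they fall naturally under other surgical procedures.

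The purpose in Section 1.2 is 6-month safety and efficacy data for a 510(k). Controls exit or cross over at 6 weeks, so the later ETDQ-7 change has no comparator and is judged by its size. It is the only longer-term symptom-score endpoint.

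**Working it through.** **1. The plan's own figure.** The planning values used below come from Section 2.6: changes of -2.15 (dilation) and -0.85 (control), SD 1.3, 1-sided alpha 0.025, 80% power. The difference is 2.15 - 0.85 = 1.30. For a two-sample t-test the noncentrality is (1.30/1.3)/√(2/n). At n = 16 per arm it is 2.83 and power is 78.1%; at n = 17 it is 2.92 and power is 80.7%. The stated 17 per arm (34 in total) is reproduced and is not in question.

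**2. Effect on the later mean change.** Let f be the share of dilated subjects with further surgery and m their mean change before it. The documents give neither, so both are assumptions. Assume also that all other subjects average -2.15 and that operated subjects reach -2.15 after surgery.

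- As-observed mean: -2.15
- Mean with the pre-surgery change kept: (1 - f) × (-2.15) + f × m
- Gap between the two: f × (2.15 + m)

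With m = 0 the gap is f × 2.15; with m = -0.85 it is f × 1.30.

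| f | Mean kept, m = 0 | Gap | Mean kept, m = -0.85 | Gap |
|---|---|---|---|---|
| 5% | -2.04 | 0.11 | -2.09 | 0.07 |
| 10% | -1.94 | 0.22 | -2.02 | 0.13 |
| 20% | -1.72 | 0.43 | -1.89 | 0.26 |
| 30% | -1.51 | 0.65 | -1.76 | 0.39 |

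The range is 0.07 (unrounded 0.065) to 0.65 (unrounded 0.645) points, or 3% to 30% of 2.15. For scale, the crossover rule in Section 2.9.5 uses 0.4 points as its cut for change.

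**3. Effect on the secondary test.** Take 25 dilated subjects, the minimum with 6-month data in Section 2.4, and assume SD 1.3 for within-group change. At the least favourable mean in the table, -1.505, the paired noncentrality is 1.505/(1.3/√25) = 5.79 and power at 2-sided 0.05 is above 99.9%. Mixing two groups also widens the SD: √(1.3² + 0.3 × 0.7 × 2.15²) = 1.63. The noncentrality is then 1.505/(1.63/5) = 4.6 and power is still about 99%. Significance would hardly be affected.

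**4. Where each kind of further surgery is counted.**

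| Further surgery for lack of relief | Revision rate | Complication rate |
|---|---|---|
| Repeat dilation of a treated tube | Yes | Only if tied to a related SAE by 6 months |
| First dilation of the other ear | No | Same condition |
| Ear tubes or other ENT surgery | No | Same condition |

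The surgical criterion for an SAE in Section 6.2 concerns injury, not lack of relief. If every further operation were ear tubes, the revision rate would be 0% whatever f was.

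**The case against.** **Counting all scores is a legitimate choice.** Change from baseline whatever care follows is a treatment-policy estimand. Carrying the last pre-surgery score forward freezes early scores and has its own bias. This stands, and it is why the remedy should accompany the as-observed analysis and not replace it. It does not excuse leaving the choice unstated.

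**The size is assumed.** This also stands. The surgery rate, the pre-surgery change and recovery to -2.15 are all suppositions.

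A reader might infer more than the documents support:

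- *Failures are counted as successes.* There is no responder endpoint. The effect is on a mean, only at visits after the surgery; scores from earlier visits stay as they were.
- *The 6-week primary comparison is biased because only controls are barred from surgery.* Early surgery in the dilation arm is possible, and Table 1 collects it at 6 weeks. But the advised wait covers healing of up to 3 months, and Section 2.9.6 disallows concomitant procedures for all subjects. The comparison is largely spared.
- *Section 3.3 contradicts Section 2.9.8.* Section 3.3 concerns concomitant procedures. Exclusion criterion 2 ties these to enrollment or the procedure, Section 2.9.6 extends the bar to the control period, and later surgery for lack of relief has its own section. The passages can be read together.
- *Other surgery counts nowhere.* It can enter the complication rate through a related SAE, and it is recorded on a CRF.
- *ETDQ-7 is the only longer-term efficacy evidence.* Tympanometry, Valsalva, otoscopy, EQ-5D and ear infections are also followed to 12 months.

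**Conclusion.** The point holds for the secondary ETDQ-7 change at 3, 6 and 12 months and for the reporting of retreatment. No sentence says outright that post-surgery scores count; this follows from the definition in Section 2.10.1 and the absence of any exception. Under the stated assumptions the flattering effect is 0.07 to 0.65 points. It would be smaller if surgery were rarer than 5% or helped less than assumed. The harm is that a figure offered as the result of dilation may partly be the result of later operations, while the revision rate understates how many subjects needed them. The sample size and the conclusion of the secondary test are not called into question. This is a matter of analysis and reporting; no view is taken on which surgery should be allowed or when.

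**What to change.** 1. In Section 2.7, state that the as-observed mean change includes scores after further surgery. Pre-specify beside it, for the 3-, 6- and 12-month visits, an analysis that replaces any score after a revision dilation or other ETD or ear surgery with the subject's last score before that surgery, or with no change from baseline. State in advance which of the two is used. The analysis should not be carried over to the 6-week score without comment: no ETDQ-7 is scheduled between baseline and that visit, so the last earlier score is the baseline and the rule would assign zero change.
2. Next to the revision rate, report the percent of dilated subjects with any further ETD or ear surgery, by type: repeat dilation, first dilation of the other ear, ear tubes, other.

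Both use the Revision Dilation/Additional Surgery CRF already in the plan. There are no new data, visits or subjects. The cost is slightly more analysis, and the reported figures may look slightly less favourable.
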